9.4 DMID Safety Oversight

DMID (medical officer, medical monitor and clinical project manager), the Protocol Chair, the UAB Central Unit, and an independent safety monitor (ISM) with expertise in pharmacology will:

- Monitor ganciclovir systemic exposures achieved with the clinical administration of ganciclovir.
- Review the safety information when a halting rule is met.
- Review AESIs on a regular basis.

9.5 FDA MedWatch Adverse Event Reporting Program

Reporting of adverse events related to drug administration is not part of the protocol. The reporting is in support of the FDA post-marketing safety surveillance program, and is encouraged.

The FDA MedWatch adverse event reporting program allows health care professionals to voluntarily report a serious adverse event, product quality problem or product use error that is suspected to be associated with the use of an FDA-regulated drug, biologic, medical device or dietary supplement. This system is for the reporting of adverse events noted spontaneously in the course of clinical care, and not for events that occur during clinical trials under an Investigational New Drug (IND) application.

The MedWatch Website, <http://www.fda.gov/Safety/MedWatch/HowToReport/ucm085568.htm> can be used to voluntarily report a serious adverse event, product quality problem or product use error that is suspected to be associated with the use of an FDA-regulated drug, biologic, medical device, dietary supplement or cosmetic. FDA uses these data to maintain safety surveillance of all FDA-regulated products. A health care professional report may be the critical action that prompts a modification in use or design of the product, improves the safety profile of the drug or device and leads to increased patient safety.

10 CLINICAL MONITORING

10.1 Site Monitoring Plan

Site Monitoring will be conducted to ensure that human subject protection, study procedures, laboratory procedures, study intervention administration, and data collection processes are of high quality and meet sponsor, GCP/ICH, and regulatory guidelines, and that the study is conducted in accordance with the protocol and study manuals. NIAID/ DMID, the sponsor of this study, or its designee will conduct site monitoring visits as detailed in the monitoring plan. A Clinical Monitoring Plan will be developed to include specifics about the monitoring, including a description of the number and type of subjects monitored, frequency of visits, tasks completed during the visits, and the different types of visits that will be used during the monitoring. The monitoring plan will be a risk based assessment.

Site visits typically may be made at standard defined intervals. More frequent sites visits may be made if needed. Monitoring visits will include, but are not limited to, review of regulatory files, case report forms, informed consent forms, medical and laboratory reports, and protocol compliance. Study monitors will meet with investigators to discuss any problems and actions to be taken and document visit findings and discussions.

Every effort will be made to maintain the anonymity and confidentiality of subjects during this study. However, because of the experimental nature of this sampling study, the Investigator agrees to allow representatives of the sponsor as well as authorized representatives of the Food and Drug Administration, or other Regulatory agencies or the UAB Central Unit, to inspect the facilities used in this study and to inspect, for purposes of verification, the hospital or clinic records of all subjects enrolled into this.

11 STATISTICAL CONSIDERATIONS

11.1 Study Hypotheses

Our primary hypothesis is that ganciclovir pharmacokinetics and pharmacodynamics in premature infants with postnatally or congenitally acquired CMV infection differ from those in term neonates and older infants.

11.2 Sample Size Considerations

The primary outcome used for power analysis is the area under the curve for 12 hours (AUC12) following 6 mg/kg of ganciclovir. In a one-way ANOVA design, we would like to compare the means of 4 groups (see below) with sample sizes of approximately 8, 8, 8, and 8 (32 total subjects enrolled across the four cohorts). If the means of the AUC12 of the 4 groups are 20, 20, 30, and 35 assuming a common standard deviation of 10, these mean differences (equivalent to an effect size of 0.72) will be detected at 83% power using an F test with 0.05 level of significance. In order to look at other possible scenarios, we provide the table below that looks at other standard deviation values, its corresponding effect size given the differences in means as described above, and the power of detecting such a difference/effect size. If estimating the AUC without regard to the groups, the margin of errors associated with a 95% confidence interval assuming different standard deviation values and a sample size of 32 are given in the table below.

Standard Deviation	S=8	S=9	S=10	S=11
Effect Size	0.81	0.72	0.64	0.59
Power	96%	91%	83%	75%
Margin of Error	2.33	2.62	2.91	3.20

The above parameter values were hypothesized based on results from other studies.^{25,34} It is worth noting that there are no PK data in this population and the results are likely to be different from other studies due to the maturational changes.

Following enrollment, subjects will be stratified by gestational age and by chronologic age as follows: 1) \leq 27 weeks 6 days gestational age at birth and \leq 30 days chronologic age at study enrollment; 2) \leq 27 weeks 6 days gestational age at birth and $>$ 30 days chronologic age at study enrollment; 3) \geq 28 weeks 0 days gestational age at birth and \leq 30 days chronologic age at study enrollment; 4) \geq 28 weeks 0 days gestational age at birth and $>$ 30 days chronologic age at study enrollment. The total sample size across these four cohorts is 32 subjects. Enrollment of an additional 2-3 subjects may be allowed for operational reasons. If the 32

subjects enrolled are not balanced across the 4 groups, we instead will look at the correlation between gestational age at birth. With 32 subjects, the margin of errors of a 95% confidence interval for estimating the correlation given the observed correlation values are given below.

Correlation	0.4	0.5	0.6	0.7
Margin of Error	0.6	0.542	0.47	0.38

Data will be collected on standardized case report forms. Standard non-compartmental techniques will be used initially to estimate pharmacokinetic parameters derived from the ganciclovir concentration-time data. The resource utilized for pharmacokinetic analysis is WinNonlin version 5.3, Pharsight Corporation, Mountain View, CA.

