11.4 Final Analysis Plan

Primary analysis: To compare the ganciclovir pharmacokinetics and pharmacodynamics as measured by AUC₁₂ in premature infants with postnatally or congenitally acquired CMV infection differ from those in term neonates and older infants, we will construct 95% confidence intervals around the mean AUC₁₂ for the subjects in this study and compare these means across the groups. If there are not enough subjects in the groups, we will use the actual gestational age and correlate it with the AUC₁₂ by computing correlation coefficients and a fitting regression model. Additional pharmacokinetic parameters that compose analyses for secondary endpoints include Cmax, T1/2, CL, and VD. For measures that are repeated over time, we will utilize mixed models for repeated measures. In addition to being able to compare these outcomes for the different groups, we can also look into how these measures change over time and adjust for covariates.

Ganciclovir pharmacokinetic parameters will initially be determined using non-compartmental analysis (WinNonlin v5.3) for each individual subject. The parameters (AUC₁₂, CL, Vd, etc.) will be summarized and further used for exploratory pharmacodynamic analysis. We will also apply pharmacokinetic models to the concentration-time data, either individually or using a population approach. We may also pool these data with prior CASG 109 PK data in order to have a more robust covariate analysis across a wider range of ages.

The second pharmacokinetic analysis will utilize either population pharmacokinetic or individual modeling approaches, depending upon how much data we actually are able to collect and the nature of those data. Concentration-time data will be analyzed using nonlinear mixed-effects in ADAPT 5.0. If a population approach is employed, this will give us the opportunity to explore

relationships between ganciclovir exposure and multiple covariates, such as gestational age, weight, renal function, etc.

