APPENDIX B

DATA ANALYSIS PLAN

Study Hypotheses

Our primary hypothesis is that ganciclovir pharmacokinetics and pharmacodynamics in premature infants with postnatally or congenitally acquired CMV infection differ from those in term neonates and older infants.

Sample Size Considerations

The primary outcome used for power analysis is the area under the curve for 12 hours (AUC12) following 6 mg/kg of ganciclovir. In a one-way ANOVA design, we would like to compare the means of 4 groups with sample sizes of 8, 8, 8, and 8. If the means of the AUC12 of the 4 groups are 20, 20, 30, and 35 assuming a common standard deviation of 10, these mean differences (equivalent to an effect size of 0.72) will be detected at 83% power using an F test with 0.05 level of significance. In order to look at other possible scenarios, we provide the table below that looks at other standard deviation values, its corresponding effect size given the differences in means as described above, and the power of detecting such a difference/effect size.

Standard Deviation	S=8	S=9	S=10	S=11
Effect Size	0.81	0.72	0.64	0.59
Power	96%	91%	83%	75%

The above parameter values were hypothesized based on results from other studies.^{25,34} It is worth noting that there are no PK data in this population and the results are likely to be different from other studies due to the maturational changes.

Subjects will be stratified by gestational age and by chronologic age as follows: 1) \leq 27 weeks 6 days gestational age at birth and \leq 30 days chronologic age at study enrollment; 2) \leq 27 weeks 6 days gestational age at birth and $>$ 30 days chronologic age at study enrollment; 3) \geq 28 weeks 0 days gestational age at birth and \leq 30 days chronologic age at study enrollment; 4) \geq 28 weeks 0 days gestational age at birth and $>$ 30 days chronologic age at study enrollment.

Data will be collected on standardized case report forms. Standard non-compartmental techniques will be used initially to estimate pharmacokinetic parameters derived from the ganciclovir concentration-time data. The resource utilized for pharmacokinetic analysis is WinNonlin version 5.3, Pharsight Corporation, Mountain View, CA.

Planned Interim Analyses

There are no planned interim analyses or safety reviews for this trial.

Final Analysis Plan

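### The four cohorts cross gestational age with chronologic age, but no planned analysis of AUC12 separates the two ages

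*Protocol*

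**What the plan says.** Protocol 11.2 states that "subjects will be stratified by gestational age and by chronologic age as follows". The four cohorts are the combinations of gestational age at birth (up to 27 weeks 6 days, or 28 weeks 0 days and above) and chronologic age at enrollment (up to 30 days, or more than 30 days). This is a 2x2 layout.

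The power statement treats the cohorts as four unlabelled groups: "In a one-way ANOVA design, we would like to compare the means of 4 groups (see below". The target is about eight infants per cohort, 32 in all. The assumed values follow: "If the means of the AUC12 of the 4 groups are 20, 20, 30, and 35 assuming a common standard deviation of 10". On these values, the protocol says, the differences between cohorts "will be detected at 83% power using an F test with 0.05 level of significance". SAP Appendix B repeats the design: "In a one-way ANOVA design, we would like to compare the means of 4 groups". Neither document says which mean belongs to which cohort.

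For the analysis, Protocol 11.4 builds 95% confidence intervals for mean AUC12 and will "compare these means across the groups". If groups are too small, it correlates and regresses AUC12 on gestational age. SAP Appendix B names mixed models for repeated measures, without listing terms. Both documents allow adjustment for unspecified covariates. Both also describe a possible population PK analysis, whose example covariates are gestational age, weight and renal function. Chronologic age is not named as a covariate in either.

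**The concern.** The cohort definitions imply an interest in two kinds of maturity: how early the infant was born and how long it has lived since. Protocol 2.1 gives direct evidence on the second. In five neonates sampled about 30 days apart, clearance nearly doubled and AUC12 fell by almost half. Protocol 2.2 says the results will inform dosing parameters for a later study.

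A three-degree-of-freedom F test does not say whether gestational or chronologic age is behind a difference between cohorts. If nothing else is pre-specified, attribution rests on informal reading of four intervals from about eight infants each, or on model choices made after the data are seen. The fallback makes this worse, because it drops the factor for which the protocol cites within-infant evidence. A reader may also take 83% as the power to detect an effect of each age, which it is not.

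**Working it through.** **Inputs.** From Protocol 11.2 and SAP Appendix B: means 20, 20, 30, 35; common SD 10; eight per cohort (N = 32); alpha 0.05. Error degrees of freedom are 32 − 4 = 28. Power is taken from the noncentral F distribution.

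**1. The plan's own figure.** The grand mean is (20 + 20 + 30 + 35)/4 = 26.25. The squared deviations are 39.0625, 39.0625, 14.0625 and 76.5625, which sum to 168.75. The noncentrality is λ = 8 × 168.75/10² = 13.5. With 3 and 28 degrees of freedom, power is 83.1%, so the stated 83% is reproduced. SDs of 8, 9 and 11 give 96.2%, 90.6% and 74.7%, matching the table's 96%, 91% and 75%.

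The effect size is f = √(168.75/4)/SD = 6.495/SD, or 0.65 at SD 10. The sentence's "equivalent to an effect size of 0.72" belongs to SD 9. This is a separate slip and does not affect the 83%.

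**2. Splitting the same 3 degrees of freedom.** In a balanced 2x2 with interaction, the error degrees of freedom stay at 28:

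- Main effect with difference d (16 vs 16): λ = 32 × (d/2)²/SD².
- Interaction with difference of differences D: λ = 32 × (D/4)²/SD².

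Taking the means in listed cohort order, which is an assumption:

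| Effect | Contrast | λ | Power, alpha 0.05 | Power, alpha 0.025 |
|---|---|---|---|---|
| Gestational age | 32.5 − 20 = 12.5 | 12.5 | 92.7% | 87.1% |
| Chronologic age | 27.5 − 25 = 2.5 | 0.5 | 10.5% | 6.1% |
| Interaction | (35 − 30) − (20 − 20) = 5 | 0.5 | 10.5% | 6.1% |

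The three λ values add to 13.5, the omnibus total.

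**3. Other assignments.** Four cells can be split into two pairs in exactly three ways, and these correspond to the two main effects and the interaction. Whichever split separates {20, 20} from {30, 35} has λ = 12.5, and the other two have 0.5 each. The 92.7% can therefore fall on gestational age, chronologic age or the interaction. The remaining two effects always have 10.5%.

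**4. Detectable main effect.** At SD 10, 16 vs 16 and alpha 0.05, 80% power needs d of about 10.3. A main effect of 2.5 would need about 508 infants.

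**5. When the omnibus test does better.** Two further patterns, with SD 10 and eight per cohort:

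- One cohort differs (35, 20, 20, 20): λ = 8 × 168.75/100 = 13.5, omnibus 83.1%. Each main effect has d = 7.5 and λ = 4.5, giving 53.5%.
- Both ages contribute equally (35, 27.5, 27.5, 20): λ = 8 × 112.5/100 = 9, omnibus 64.4%. Each main effect again has 53.5%.

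**The case against.** A reader might infer that the one-way test simply loses power and should be replaced. The documents do not support that. The gain from 83.1% to 92.7% arises only if one main effect carries nearly all the difference, and it shrinks to 87.1% if two main effects are each tested at 0.025. If only one cohort differs, or both ages contribute equally, the omnibus test is the stronger. If the plan's means fall as a crossover, both main effects have 10.5% while the omnibus test keeps 83.1%.

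A reader might also infer that the 83% says nothing about chronologic age. That depends on an assignment of means that the plan does not give. Listed order puts the lowest AUC12 in the infants born earliest. Protocol 2.1, where AUC12 fell with postnatal age, would also fit 35 and 30 in the younger-age cohorts and 20 and 20 in the older. The 83% would then come almost wholly from chronologic age.

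Two further objections have some force. Attribution to one age is not the stated objective, which is to define the pharmacokinetics; the hypothesis compares premature infants with term neonates and older infants. And the F test appears only in the sample-size text. Cohort intervals, covariate adjustment and population PK could give some attribution. But those routes are optional or unspecified, none names chronologic age, and the plan itself chose to stratify on both ages. The gap in pre-specification remains.

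**Conclusion.** The concern holds as a gap in pre-specification and in how the power is described. The 83% is right for the test named. What is missing is any stated analysis that separates the two ages defining the cohorts, and any statement of power for each. On the plan's own means, one of the three component effects has 92.7% power (87.1% at alpha 0.025) and the other two have 10.5% (6.1%). Since there are two age factors, at least one has only about 10% whatever the assignment.

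These figures assume the plan's means, a common SD of 10, normal errors and eight infants per cohort. The protocol says approximately eight and foresees imbalance, which would reduce the precision of the 16-vs-16 contrasts. Whether the two-factor tests are more or less powerful than the omnibus test cannot be settled from the documents, so this point is not a reason to demote the omnibus test.

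**What to change.** - **Protocol 11.2 and SAP Appendix B, sample size:** keep the omnibus F test and its 83%. State which assumed mean belongs to which cohort. Add the detectable main effect (about 10.3 at SD 10 for 80% power, 16 vs 16, alpha 0.05) and the power for each factor under the stated assignment.
- **Protocol 11.4 and SAP Appendix B, analysis:** fit AUC12 with gestational-age stratum, chronologic-age stratum and their interaction. Report each effect with a 95% CI. If the main effects are tested formally, state the alpha rule, for example 0.025 each.
- **Fallback for unbalanced cohorts:** include both gestational and chronologic age in the regression.

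The cost is wording only: same infants, same samples, same 28 error degrees of freedom. The downside is that the plan will show much lower power than 83% for at least one factor, and two main-effect tests bring a multiplicity rule that the single omnibus test does not need.

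### Protocol 11.2: the 95% margin of error for the overall mean AUC12 is a 90% half-width built on the within-cohort SD, so it is narrower than the ungrouped 95% interval it describes

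*Protocol*

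**What the plan says.** Protocol 11.2 sizes the study on a one-way ANOVA of AUC12 across four cohorts defined by gestational and chronologic age, with "sample sizes of approximately 8, 8, 8, and 8 (32 total subjects enrolled across the four cohorts". The scenario is "If the means of the AUC12 of the 4 groups are 20, 20, 30, and 35 assuming a common standard deviation of 10", and the differences "will be detected at 83% power using an F test with 0.05 level of significance".

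A table then varies the SD over 8, 9, 10 and 11. One SD header serves three result rows: effect size ("0.81 0.72 0.64 0.59"), power (96%, 91%, 83%, 75%) and margin of error ("2.33 2.62 2.91 3.20"). The text introduces the margin row as follows: "If estimating the AUC without regard to the groups, the margin of errors associated with a 95% confidence interval assuming different standard deviation values", with a sample size of 32. It does not say whether S in that row is the within-cohort or the overall SD.

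On analysis, Protocol 11.4 says "we will construct 95% confidence intervals around the mean AUC₁₂ for the subjects in this study and compare these means across the groups". It does not define how an overall mean across cohorts would be estimated. SAP Appendix B repeats the power table without a margin row. SAP Appendix C (3.3.4.2) stops enrolment in a cohort once it has eight infants.

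**The concern.** The primary objective is to define ganciclovir pharmacokinetics in infants born before 32 weeks, and AUC12 is the primary endpoint. The margin row is the only statement in either document of how precisely the overall mean AUC12 will be known.

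That row is described as a 95% interval that sets cohort aside. Its figures look too small for 95% with 32 infants. They also rest on an SD that, in the rows above it, is the spread around four different cohort means. Once cohort is ignored, the distance between those means becomes part of the spread among the 32 values. The differences that generate 83% power should therefore also widen the ungrouped interval, and the table does not show this. A reader would expect about ±2.9 at S = 10, whereas the interval described would be nearer ±4.3.

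**Working it through.** **Inputs (all Protocol 11.2):** cohort means 20, 20, 30, 35; S = 8, 9, 10, 11; n = 32, eight per cohort; 95% interval for the overall mean.

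**1. What S is in the power row.** The grand mean is (20 + 20 + 30 + 35)/4 = 26.25. The variance of the cohort means is (6.25² + 6.25² + 3.75² + 8.75²)/4 = 168.75/4 = 42.19, an SD of 6.50. Effect size f = 6.495/S gives 0.812, 0.722, 0.650 and 0.590. The noncentral F with 3 and 28 df and noncentrality 32f² gives power of 96.2%, 90.6%, 83.1% and 74.7%. The printed powers reproduce, so S there is the within-cohort SD. (The prose attaches effect size 0.72 to an SD of 10, while the table puts it at S = 9. That is a separate slip and does not affect what follows.)

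**2. Reproducing the margin row.** 1.645 × S/√32 gives 2.33, 2.62, 2.91 and 3.20, which matches all four columns. The row therefore uses the same S with the two-sided 90% multiplier.

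**3. Correcting each element.** Total SD = √(S² + 42.19), at equal cohort shares.

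| | S=8 | S=9 | S=10 | S=11 |
|---|---|---|---|---|
| Printed | 2.33 | 2.62 | 2.91 | 3.20 |
| Multiplier only: 1.960 × S/√32 | 2.77 | 3.12 | 3.46 | 3.81 |
| Multiplier only: t (31 df) × S/√32 | 2.88 | 3.24 | 3.61 | 3.97 |
| Total SD | 10.30 | 11.10 | 11.92 | 12.77 |
| SD only: 1.645 × total SD/√32 | 3.00 | 3.23 | 3.47 | 3.71 |
| Both, normal | 3.57 | 3.85 | 4.13 | 4.43 |
| Both, t (31 df) | 3.72 | 4.00 | 4.30 | 4.61 |
| Widening from the SD alone (total SD/S) | 29% | 23% | 19% | 16% |

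At S = 10 the ratio 4.13/2.91 = 1.42 splits almost equally: 1.960/1.645 = 1.19 from the multiplier and 11.92/10 = 1.19 from the SD.

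**4. Width by simulation at S = 10 (40,000 trials).** The mean half-width of the ungrouped 95% t interval was 4.28 with exactly eight per cohort and 4.27 with cohort membership at random in equal expected shares. The width hardly depends on how the cohorts fill.

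**5. Coverage depends on the allocation.**

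- *Exactly eight per cohort.* The standard error of the overall mean is S/√32 (1.77 at S = 10), because differences between cohort means do not vary from trial to trial. A margin of 1.960 × S/√32 then covers 95%, the printed margins cover 90%, and the ungrouped t interval over-covers at about 98%.
- *Shares left to chance.* The standard error is total SD/√32, and 1.960 × S/√32 covers 2Φ(1.960 × S/total SD) − 1, about 87%, 89%, 90% and 91%. The printed margins cover about 80%, 82%, 83% and 84%.

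**6. Sensitivity to the assumed means and shares, S = 10.** With equal cohort means the total SD is 10 and the t margin is 3.61. With illustrative shares of 0.4/0.4/0.1/0.1 the between-cohort variance is 26.25 and the margin is 2.0395 × √126.25/√32 = 4.05. With shares of 0.1/0.4/0.1/0.4 it is 51 and the margin is 2.0395 × √151/√32 = 4.43. None of these reaches as low as 2.91.

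**The case against.** The strongest reply is that S is the right SD under the design as planned. With eight infants per cohort, and the SAP closing each cohort at eight, between-cohort differences add nothing to the sampling variance of the equally weighted mean. Correcting 1.645 to 1.960 then gives a valid 95% margin, and the total-SD margin would understate the precision available.

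That is correct, and it limits the point. A reader might infer that power and margin in one column can never both hold, that the true coverage is 87–91%, or that the whole gap from 2.91 to 4.30 comes from the SD. The documents support none of these. Power of 83% and a margin of 1.960 × S/√32 coexist for a cohort-stratified interval. The coverage loss needs cohort shares that are not fixed. About half of the gap is the multiplier.

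The reply does not rescue the row as written. The text describes an interval that sets cohort aside, and neither document defines a stratified overall mean that would make S the right input. Nor is eight per cohort assured: the Protocol says approximately eight, permits two or three extra infants, and provides for the case in which the "subjects enrolled are not balanced across the 4 groups, we instead will look at the correlation between gestational age at birth".

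It is also fair that the text never says S in the margin row is the within-cohort SD. If it was meant as the total SD, one header carries two meanings and still needs correcting, and the multiplier error stands regardless. Finally, the row does not set the sample size, and the reported interval will come from observed data. Only the planning statement is affected.

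**Conclusion.** The margin row is wrong as described. The multiplier error depends on no assumption about the cohorts: the printed figures are 90% half-widths, and at S = 10 the 95% margin with the same SD is 3.46 (normal) or 3.61 (t, 31 df), not 2.91.

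The SD point is real but conditional. It assumes that S keeps the meaning it has in the power row, that the cohort means are 20, 20, 30 and 35, and that cohort shares are equal. On that basis the ungrouped 95% t interval is about ±3.72, ±4.00, ±4.30 and ±4.61, of which the SD accounts for a widening of 29%, 23%, 19% and 16%. This is a statement about the width of the ungrouped interval, not about lost coverage under the planned allocation; with eight per cohort that interval is conservative.

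The power row and the sample size of 32 are unaffected.

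**What to change.** Correct the multiplier in either case, and state which SD and which interval the row refers to. Then choose one:

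- **(a) Keep the ungrouped interval.** In Protocol 11.2 restate the row as 3.72, 4.00, 4.30 and 4.61 (t, 31 df), with a note that it assumes the stated cohort means and equal shares.
- **(b) Use a stratified interval.** In Protocol 11.2, Protocol 11.4 and SAP Appendix B, define the overall mean as the equally weighted mean of the four cohort means, with the pooled within-cohort SD on 28 df. Relabel the row and print 2.90, 3.26, 3.62 and 3.98. These hold if about eight infants per cohort are obtained; otherwise the standard error is (S/4) × √(1/n₁ + 1/n₂ + 1/n₃ + 1/n₄), which equals S/√32 at eight each.

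Neither needs more infants or data. Option (a) costs one table row with less favourable figures. Option (b) costs a sentence in each place and gives an estimate for an equal mix of the four cohorts rather than for the mix actually enrolled.

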The appropriate dose of intravenous ganciclovir for premature babies has not been studied. Previous studies of ganciclovir have indicated that the area-under-the-concentration curve (AUC) of ganciclovir is most closely related to virologic treatment success.²³ Data from an National Institute of Allergy and Infectious Diseases (NIAID) CASG Phase II study of intravenous ganciclovir (6 mg/kg/dose q 12 hrs) in term neonates with symptomatic congenital CMV disease revealed a median AUC₁₂ of 27 μ gxh/mL (mean AUC₁₂=32.3+13.7 μ gxh/mL, range 17.2 to 55.9 μ gxh/mL, n=13).²⁴ A more recent CASG investigation of oral valganciclovir included comparative pharmacokinetic data following 6 mg/kg/dose every 12 hrs of intravenous ganciclovir. The mean AUC₁₂ in young neonates (median age: 16.5 days) on the second day following study enrollment was 38.2 μ gxh/mL (median: 25.5 μ gxh/mL), but the coefficient of variation was large (112).²⁵ In five neonates in whom pharmacokinetic sampling was performed on day 4 and day 34 of intravenous ganciclovir therapy, ganciclovir clearance nearly doubled and AUC₁₂ reduced by almost half over the 30 day interval,²⁵ suggesting that maturational changes may be occurring rapidly in early life which may affect ganciclovir dosing. No data exist on ganciclovir dosing in very premature babies, who are at greatest risk for CMV disease.

due to the absence of transplacental antibodies. Notably, acyclovir must be dose-adjusted based upon renal function such as that which can occur with prematurity.²⁶

The CASG and the UAB Central Unit have had significant success in performing multi-center pharmacokinetic and pharmacodynamic studies with both ganciclovir and valganciclovir in infants during the first month of life.^{21,22,25,27-30} In this study, this experience will be utilized to further define the utility of this drug in very premature children.

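### Protocol 11.2 labels 90% margins for mean AUC12 as 95%, prints full interval widths as correlation margins, and gives effect size 0.72 where its own inputs give 0.65

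*Protocol*

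**What the plan says.** Protocol 11.2 plans a one-way ANOVA of AUC12 "with sample sizes of approximately 8, 8, 8, and 8 (32 total subjects enrolled across the four cohorts"). The planning scenario is: "If the means of the AUC12 of the 4 groups are 20, 20, 30, and 35 assuming a common standard deviation of 10". The text then states that "these mean differences (equivalent to an effect size of 0.72) will be detected at 83% power". SAP Appendix B (Sample Size Considerations) repeats that statement.

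The table under it gives, for SD 8, 9, 10 and 11:
- effect sizes 0.81, 0.72, 0.64 and 0.59
- powers 96, 91, 83 and 75%
- in the protocol only, margins of error 2.33, 2.62, 2.91 and 3.20, introduced as "the margin of errors associated with a 95% confidence interval assuming different standard deviation values and a sample size of 32" when the groups are ignored.

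A second protocol table, also absent from the SAP, gives "the margin of errors of a 95% confidence interval for estimating the correlation given the observed correlation values". Its values are 0.6, 0.542, 0.47 and 0.38 for observed correlations of 0.4, 0.5, 0.6 and 0.7 with 32 infants.

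Both margin rows relate to analyses in protocol 11.4. Its primary analysis begins "we will construct 95% confidence intervals around the mean" AUC12, and its fallback reads: "If there are not enough subjects in the groups, we will use the actual gestational age and correlate it with the" AUC12.

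**The concern.** Three figures in 11.2 do not fit their labels.

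- **AUC12 margins.** They look too small for 95% intervals at n = 32.
- **Correlation margins.** They cannot be plus/minus margins, because a correlation cannot exceed 1, yet 0.5 + 0.542, 0.6 + 0.47 and 0.7 + 0.38 all do.
- **Effect size.** The text attaches 0.72 to SD 10, while the table beneath puts 0.72 under SD 9.

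The protocol says that no PK data exist in this population, so the stated precision is a main way to judge what 32 infants can deliver. The two margin errors run in opposite directions. The AUC12 row overstates precision. The correlation row understates it about twofold and, taken literally, suggests that an observed correlation of 0.4 or 0.5 could not be told from zero.

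**Working it through.** **Inputs (protocol 11.2).** n = 32, four groups of 8; means 20, 20, 30, 35; SD 8, 9, 10, 11; α = 0.05; correlations 0.4 to 0.7.

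**1. Margins for mean AUC12.** Margin = multiplier × SD/√32, with √32 = 5.657.

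| | SD 8 | SD 9 | SD 10 | SD 11 |
|---|---|---|---|---|
| Printed | 2.33 | 2.62 | 2.91 | 3.20 |
| Implied multiplier, printed ÷ (SD/√32) | 1.648 | 1.647 | 1.646 | 1.646 |
| 90% normal (1.645) | 2.326 | 2.617 | 2.908 | 3.198 |
| 95% normal (1.960) | 2.772 | 3.118 | 3.465 | 3.811 |
| 95% t, 31 df (2.0395) | 2.884 | 3.245 | 3.605 | 3.966 |

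The 90% normal multiplier reproduces all four entries to two decimals, and neither 95% version does. The printed margins have 90.0 to 90.1% coverage by the normal, or about 89% by t with 31 df. The mislabelling alone makes the 95% margins 1.960/1.645 = 1.19 times the printed ones. With t, the usual choice when the SD is estimated, the ratio is 2.0395/1.645 = 1.24. For the printed margins to be true 95% margins, 48 infants would be needed by t (46 by the normal).

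**2. Correlation margins.** Fisher-z limits: tanh(atanh r ± 1.96/√(32 − 3)).

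| r | Printed margin | r ± printed margin | 95% limits | Full width | Distance below / above r |
|---|---|---|---|---|---|
| 0.4 | 0.6 | −0.20 to 1.00 | 0.060 to 0.657 | 0.597 | 0.340 / 0.257 |
| 0.5 | 0.542 | −0.04 to 1.04 | 0.183 to 0.723 | 0.539 | 0.317 / 0.223 |
| 0.6 | 0.47 | 0.13 to 1.07 | 0.318 to 0.785 | 0.467 | 0.282 / 0.185 |
| 0.7 | 0.38 | 0.32 to 1.08 | 0.465 to 0.843 | 0.378 | 0.235 / 0.143 |

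The printed values agree with the full widths to within about 0.003. The half-widths are 0.299, 0.270, 0.233 and 0.189, about half of what is printed. Other standard-error formulas do not rescue the label: with √((1 − r²)/30) and t on 30 df, the half-widths are 0.342, 0.323, 0.298 and 0.266.

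**3. Effect size and power.** The grand mean is (20 + 20 + 30 + 35)/4 = 26.25. The squared deviations are 39.0625, 39.0625, 14.0625 and 76.5625. Their mean is 168.75/4 = 42.1875, with square root 6.495. So f = 6.495/SD, and power comes from the noncentral F with 3 and 28 df and noncentrality 32f².

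| | SD 8 | SD 9 | SD 10 | SD 11 |
|---|---|---|---|---|
| f, computed | 0.812 | 0.722 | 0.6495 | 0.590 |
| f, printed in table | 0.81 | 0.72 | 0.64 | 0.59 |
| Power, computed | 96.2% | 90.6% | 83.1% | 74.7% |
| Power, printed | 96% | 91% | 83% | 75% |

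The power row reproduces. At SD 10 the effect size is 0.65; the table's 0.64 is 0.6495 truncated. The 0.72 in the text belongs to SD 9 and would give 90.5% power with 8 per group, not the 83% in the same sentence.

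**The case against.** The strongest reply is that nothing decided from these figures changes. The powers and n = 32 stand. The rows are planning illustrations, and the final intervals will use observed SDs and correlations. In absolute terms the AUC12 understatement is 0.55 to 0.77 (t), or 2 to 3% of the planned mean of 26.25, against assumed group differences of 10 to 15. All of this is true and limits the weight of the point.

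The link to the primary analysis also has limits. The margin row ignores the groups, whereas 11.4 compares means across them. For one group of 8 at SD 10 the 95% t margin is about 2.365 × 10/√8 = 8.4, which neither the printed nor the corrected row describes. SAP Appendix B names mixed models, not intervals, for the primary analysis. The relevance is therefore to the protocol's pooled mean and its fallback correlation.

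The correlation error is on the cautious side, and limits above 1 warn a careful reader. They do not tell that reader the right limits. The effect-size slip can be found from the table below it, but it stands in both documents. A multiplier of 1.645 also gives a one-sided 95% bound, but the text speaks of a confidence interval and a margin of error, so that reading does not save the label.

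Whether SD 8 to 11 is realistic is a separate question. The term-neonate data in protocol 2.1 (SD 13.7 at mean 32.3) correspond to SD 11.1 if the CV is held at the planned mean (13.7/32.3 × 26.25), close to the printed SD 11 column. Nothing here rests on that question.

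**Conclusion.** All three errors hold. The AUC12 margins are 90% margins; true 95% margins are 19% (normal) to 24% (t) larger. The correlation margins are full interval widths; the correct 95% limits exclude zero at every tabulated correlation, including 0.4 and 0.5. The effect size at SD 10 is 0.65, not 0.72, in both documents. The sample size and its 83% power are correct for the stated inputs.

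The figures assume 32 evaluable infants, a single pooled SD for the AUC12 margins, and the Fisher-z approximation for the correlations. These are wrong statements of what the study can estimate and should be corrected, but they do not undermine the design.

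**What to change.** **Protocol 11.2**
- Replace the AUC12 margin row with 2.88, 3.24, 3.61 and 3.97, stating that it uses t with 31 df (or with 2.77, 3.12, 3.46 and 3.81, stating that it uses the normal).
- Replace the correlation margin row with lower and upper 95% limits, since the intervals are asymmetric: 0.060 to 0.657, 0.183 to 0.723, 0.318 to 0.785 and 0.465 to 0.843.

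**Protocol 11.2 and SAP Appendix B**
- In the text, change the effect size for SD 10 from 0.72 to 0.65.
- In the table, change 0.64 to 0.65.
- Leave the power row and the 83% as they are.

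The cost is two table rows in the protocol, and one sentence and one table cell in each document. The stated AUC12 precision becomes less favourable. No infants are added and no analysis changes.
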